5. How does tobacco use, other forms of tobacco use, and/or environmental tobacco exposure affect patient's treatment toxicity, patient-reported physical and psychological symptoms, trial adherence, and therapeutic outcomes?

When patients consent to participate, they will be asked to provide a contact email address and that address along with their registration information will be sent directly from the parent trial's registration system to ECOG-ACRIN Systems for Easy Entry of Patient Reported Outcomes (EASEE-PRO), and the patient will be automatically registered into EASEE-PRO for participation. To activate their account for self-directed web entry of surveys, the system will send an activation message to the contact email address that will explain how to activate their account for self-directed web entry of surveys. After their account is activated, the patient will

be able to complete questionnaires using a secure browser interface from any web enabled computer, tablet, or mobile device.

Measures

The selected Core and Extension C-TUQ items will be assessed. The 4-item Short Form PROMIS® for anxiety and depression, the Lung Cancer Stigma Scale, and six symptom items (general pain, fatigue, nausea, cough, insomnia, shortness of breath) from FACIT (Functional Assessment of Chronic Illness Therapy) together with modifications of these same six questions to address the degree of bother associated with each symptom will be administered as well. Additionally, we will ask participants' perceptions of how smoking improves or worsens each of the six symptom experience. All these items will be compiled into Survey of Tobacco Use (STU) (baseline and follow-up).

Contents and Corresponding Questions in Survey of Tobacco Use (STU)

Dimension	Source of Measures	Baseline STU	Follow-up STU
Basic Tobacco Use Information	C-TUQ	Q1 – Q5	Q1 – Q2
Tobacco Use in Relation to Cancer Diagnosis and Treatment	C-TUQ	Q6 – Q7	Q3
Smoking Cessation, Cessation Products, and Assistance Methods	C-TUQ	Q8 – Q13	Q4 – Q9
Use of Other Products	C-TUQ	Q14	Q10
Second-Hand Smoke Exposure	C-TUQ	Q15 – Q16	Q11 – Q12
Psychological Symptoms	PROMIS Lung Cancer Stigma Scale	Q17 – Q18	Q13 – Q14
Physical Symptoms	FACIT	Q19	Q15
Sociodemographics		Q20 – 21	

NOTE: In order to minimize ambiguity and assure that patients are oriented to answer appropriately, the specific phrasing of items may vary depending specific cancer type and treatment.

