1. CHANGES IN SMOKING STATUS AND EXPOSURE. At baseline, combustible tobacco use (1a) will be characterized by smoking status (never smoker, former smoker, and current smoker based on Baseline STU Qs 1 and 5), other forms of tobacco use (1b) will be a composite variable determined by non-cigarette items (based on Baseline STU Q7 and Q14), and environmental tobacco smoke (ETS) level (1c) will be determined by current household and work exposure (Baseline STU Qs 15-16). At follow-up, combustible tobacco use (1a) will be examined by smoking status (Follow-up STU Qs 1 and 2), other forms of tobacco use (1b) will be determined by Follow-up STU Q10, and ETS level (1c) will be determined by 30 day household and work exposure (Follow-up STU Qs 11-12). We will examine tobacco use at baseline, 3 and 6 month follow-up, and change in status (abstinence in combustible tobacco, abstinence of other forms of tobacco use, and change

Rev. Add4

in exposure to smoke-free home and work) using summary statistics (frequency and proportion). We will explore the effects of sociodemographic and cancer treatment factors on smoking status using logistic regression (comparing smokers and non-smokers). We will also evaluate factors associated with changes in smoking status.

2. **TREATMENT TOXICITY.** The selected trials capture information about adverse events during treatment using NCI's Common Terminology Criteria for Adverse Events. Toxicities are measured at each treatment visit and graded according to severity, with grade 1 corresponding to mild toxicity and grade 5 signifying a lethal adverse event. We will determine each patient's worst degree toxicity across all event types and treatment visits and will compare the distribution of worst degree grades between smokers and non-smokers and between patients with environmental tobacco exposure and those without exposure using exact tests. We will also examine the distribution of worst degree grades between users with different form of tobacco use. In addition, we will explore the effects of tobacco use on dose modifications (yes vs. no) using logistic regression, with each patient's dose modification status determined across all treatment visits.

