3. **SYMPTOM BURDEN.** Tobacco variables will be conceptualized as described in the section of CHANGES IN SMOKING STATUS AND EXPOSURE. Tobacco use status (as measured at baseline, 3 and 6 month follow-up) will be compared to physical and psychological symptom burden (as measured at each corresponding time points). At 3 and 6 month follow-up, we will also examine the association between tobacco use changes and changes in symptom burden. We will explore the effects of sociodemographic and cancer treatment factors on symptom burden using repeated measures mixed effects models. As an example of statistical power, we consider the PROMIS SF-4 depression measure. We assume that 1500 patients will be enrolled across the 8 parent studies over 13 months, and that 20% are smokers. We assume that 85% of patients will have assessments at 6 months. Given groups of these sizes (26 quitters and 230 still-smokers) and standard deviation of 4.08 for the PROMIS SF-4 depression scale, there will be 83% power to detect a difference in change scores of 2.5 between groups using a two-sample t-test with Type I error of 5%. The minimally important difference for this instrument is 2.2.⁷⁹
4. **CESSATION PATTERNS AND TREATMENT.** At baseline we will explore pre-treatment combustible tobacco use patterns (STU Q6a and Q6b), quitting behaviors (STU Q13), behavioral program utilization (STU Q11) and oncology provider support (5As, STU Q12), and smoking cessation medication use (STU Q10). At follow-up we will explore post-treatment combustible tobacco use patterns (STU Q3a-Q3e), quitting behaviors (STU Q9), behavioral program utilization (STU, Q7) and oncology provider support (5As, STU Q8), and smoking cessation medication use (STU Q6). We will explore the effects of sociodemographic and cancer treatment factors on these variables. We will examine associations of quitting behaviors and behavioral and medication utilization with tobacco use status (as outlined in the section of CHANGES IN SMOKING STATUS AND EXPOSURE) at baseline and on respective 3 and 6 month tobacco outcomes. These analyses will be descriptive in nature. Summary statistics (frequency, proportions, and 95% confidence intervals) will be used.

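### Change in non-cigarette tobacco use is measured with two items at baseline but one at follow-up, so a patient can be scored abstinent without changing; the stated time frame for smoke exposure also differs between visits.

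*Combined protocol and SAP*

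**What the plan says.** The definitions are in Appendix VIII, Statistical Considerations and Analysis Plans, item 1.

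- **Other tobacco (1b), baseline:** "other forms of tobacco use (1b) will be a composite variable determined by non-cigarette items (based on Baseline STU Q7 and Q14").
- **Other tobacco (1b), 3 and 6 months:** "other forms of tobacco use (1b) will be determined by Follow-up STU Q10".
- **Environmental tobacco smoke (1c), baseline:** "environmental tobacco smoke (ETS) level (1c) will be determined by current household and work exposure (Baseline STU Qs 15-16").
- **Environmental tobacco smoke (1c), 3 and 6 months:** "ETS level (1c) will be determined by 30 day household and work exposure (Follow-up STU Qs 11-12").

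The same item says that it will summarise "change in status (abstinence in combustible tobacco, abstinence of other forms of tobacco use, and change" in home and work exposure, using frequencies and proportions. Item 3 takes its tobacco variables from item 1 and adds that at follow-up "we will also examine the association between tobacco use changes and changes in symptom burden".

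The survey contents table, in Appendix VIII and again in Section 5.6, shows which baseline and follow-up questions belong together. One row reads "Use of Other Products C-TUQ Q14 Q10". Another reads "Tobacco Use in Relation to Cancer Diagnosis and Treatment C-TUQ Q6 – Q7 Q3". The second-hand smoke row pairs Baseline Q15 and Q16 with Follow-up Q11 and Q12.

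The plan gives no rule for combining the two baseline items into the composite, and none for aligning baseline and follow-up definitions before change is computed. The wording of the survey questions is not in the documents.

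**The concern.** A change score needs the same variable at both ends. For other tobacco use, the baseline variable draws on two questions and the follow-up variable on one. Baseline Q7 has no designated non-cigarette counterpart at follow-up. Its row in the contents table points to Follow-up Q3, which the follow-up definition does not use and which item 4 assigns, as Q3a to Q3e, to combustible tobacco patterns.

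If a patient counts as a baseline user because of Q7 alone, dropping Q7 later can turn that patient into an abstainer on paper. The abstinence proportion would then mix real quitting with the change of definition. The item 3 association between change in use and change in symptoms would tend to be diluted by patients who changed nothing.

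For smoke exposure, the stated time frame moves from current to 30 days while change is reported across the two. If the questions really differ in this way, part of any apparent change would reflect the window.

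**Working it through.** **1. The plan's own figure.** The only number stated for the change analyses is the power example in item 3: 26 quitters against 230 still-smokers, SD 4.08, difference 2.5, type I error 5% (taken as two-sided), power 83%.

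- Standard error = 4.08 × √(1/26 + 1/230) = 4.08 × 0.2069 = 0.844.
- 2.5 / 0.844 = 2.96, and 2.96 − 1.96 = 1.00, so normal-approximation power is 84.2%. The noncentral t with 254 degrees of freedom gives 83.9%. Both agree with 83% to within 2 points. A one-sided test would give 90.6%, which does not fit.
- Group total: 1500 × 0.20 × 0.85 = 255, against 26 + 230 = 256.

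The figure reproduces. It is built from the assumed number of smokers, so it concerns combustible use (1a) and does not depend on the definitions of 1b or 1c.

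**2. Item matching.**

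| Variable | Baseline | Follow-up used | Match in contents table |
|---|---|---|---|
| Other tobacco (1b) | Q14 | Q10 | Same row |
| Other tobacco (1b) | Q7 | none | Row's follow-up item is Q3, not used for 1b |
| Smoke exposure (1c) | Q15, Q16, worded as current | Q11, Q12, worded as 30-day | Same row, two items each |

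The item mismatch is confined to 1b. The time-frame mismatch is stated only for 1c.

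**3. Size for other tobacco use.** Assume that either item makes a patient a baseline user, and that Q10 repeats Q14. Let x be the share of baseline users flagged by Q7 alone and q the true abstinence proportion. Then

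reported abstinence = x + (1 − x)q, an excess of x(1 − q).

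With no true change (q = 0) the false abstinence is x. The documents do not give x, so these values are assumptions:

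| Assumed x | False abstinence, Q7/Q14 to Q10 | False abstinence, Q14 to Q10 |
|---|---|---|
| 0% | 0% | 0% |
| 10% | 10% | 0% |
| 20% | 20% | 0% |
| 30% | 30% | 0% |
| 50% | 50% | 0% |

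If the composite instead required both items, a patient positive only on Q14 would be a baseline non-user and could appear as a new user at follow-up. The variables are mismatched under either rule, and pairing Q14 with Q10 removes both problems.

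**4. Direction for smoke exposure.** A 30-day window that includes the present captures at least as much exposure as a question about now. With an assumed current exposure of 20% and an assumed 30-day exposure of 20% to 30%, the apparent change with no true change runs from 20 − 20 = 0 to 30 − 20 = +10 points. If the windows do differ, the tendency is to raise follow-up exposure.

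**The case against.** The strongest reply is that the mechanism rests on text that nobody can see here. The plan says only that 1b is a composite. It states neither an either-item rule nor the denominator for abstinence. Q7 sits in a block about tobacco use around diagnosis and treatment, so it may record timing or history and add no users beyond Q14. Then x is zero and nothing is biased. This stands: the bias is conditional and its size unknown. It does not remove the definitional gap, since the plan names Q7 as part of the baseline variable and nothing replaces it at follow-up.

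On smoke exposure, a reader might infer from the question numbers that different items are used, or that the mismatch would be reported as reduced exposure. The documents support neither. Both pairs fill the same two-item row, and different numbers in a shorter follow-up form do not show different questions. A longer window would tend to raise measured exposure, not lower it. The word current may also be shorthand for the same 30-day question.

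On importance, Section 2.5 says that the tobacco data will not be analysed in this trial's clinical study report, and Appendix VIII plans a combined analysis of 8 trials. The changes in 1b and 1c are reported as summary statistics. No endpoint, test or decision of this trial is touched. This also stands, and it limits the weight of the point.

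**Conclusion.** The definition of other tobacco use changes between baseline and follow-up while abstinence is reported across the change. That much is plain from the text. Under an either-item composite, with Q10 repeating Q14 and no true change, false abstinence equals the Q7-only share of baseline users. The share cannot be obtained from the documents and may be zero. A reader might conclude that reported quit rates are biased upward as a matter of fact; the documents do not support that without the item wording, the scoring rule and the prevalences.

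For smoke exposure, the stated time frames are inconsistent and should be reconciled. The items are not shown to differ, and neither the size nor the direction of any bias is established.

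This is a minor correction to an exploratory, pooled ancillary analysis. The 83% power figure and everything in the main trial's analysis are unaffected.

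**What to change.** In Appendix VIII, item 1:

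- Derive change in other tobacco use from the paired items only, Baseline Q14 with Follow-up Q10. Keep Baseline Q7 for describing patients at baseline, and state how the baseline composite is scored.
- State one recall window for environmental smoke exposure at baseline, 3 months and 6 months, where the item wording allows it.
- In item 3, use these matched variables for the association between change in tobacco use and change in symptoms.

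For 1b this needs new plan wording and no new data. The matched baseline variable may count somewhat fewer users. The ETS change depends on what the questions actually ask. Because the ancillary plan is shared, the wording has to be agreed across the 8 parent trials.

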2.5 Exploratory Tobacco Use Objectives

- 2.5.1 To determine the effects of tobacco, operationalized as combustible tobacco (1a), other forms of tobacco (1b), and environmental tobacco exposure (ETS) (1c) on provider-reported cancer-treatment toxicity (adverse events (both clinical and hematologic) and dose modifications).
- 2.5.2 To determine the effects of tobacco on patient-reported physical symptoms and psychological symptoms.
- 2.5.3 To examine quitting behaviors and behavioral counseling/support and cessation medication utilization.
- 2.5.4 To explore the effect of tobacco use and exposure on treatment duration, relative dose intensity, and therapeutic benefit.

NOTE: Tobacco Use objectives described above are ancillary for the Tobacco Use Assessment project approved by NCI. A combined analysis of the data from the selected ECOG-ACRIN trials is planned. Data collected from the tobacco use assessment in each parent study will not be analyzed and reported in the clinical study report.

3. Selection of Patients

Each of the criteria in the checklist that follows must be met in order for a patient to be considered eligible for this study. Use the checklist to confirm a patient's eligibility. For each patient, this checklist must be photocopied, completed and maintained in the patient's chart.

In calculating days of tests and measurements, the day a test or measurement is done is considered Day 0. Therefore, if a test is done on a Monday, the Monday four weeks later would be considered Day 28.

ECOG-ACRIN Patient No. _____

Patient's Initials (L, F, M) _____

Physician Signature and Date _____

NOTE: CTEP Policy does not allow for the issuance of waivers to any protocol specified criteria (http://ctep.cancer.gov/protocolDevelopment/policies_deviations.htm). Therefore, all eligibility criteria listed in Section 3 must be met, without exception. The registration of individuals who do not meet all criteria listed in Section 3 can result in the participant being censored from the analysis of the study, and the citation of a major protocol violation during an audit. All questions regarding clarification of eligibility criteria must be directed to the Group's Executive Officer ([contact]) or the Group's Regulatory Officer ([contact]).

NOTE: Institutions may use the eligibility checklist as source documentation if it has been reviewed, signed, and dated prior to registration/randomization by the treating physician.

3.1 Eligibility Criteria for Step 0

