5.2.4 Terminology

- **Adverse Event (AE):** Any untoward medical occurrence associated with the use of an agent in humans, whether or not considered agent related. Therefore, an AE can be **ANY** unfavorable and unintended sign (including an abnormal laboratory finding), symptom, or disease temporally associated with the use of a medicinal product, whether or not considered related to the medicinal product.
- **Attribution:** An assessment of the relationship between the adverse event and the protocol treatment, using the following categories.

ATTRIBUTION	DESCRIPTION
Unrelated	The AE is clearly NOT related to treatment.
Unlikely	The AE is doubtfully related to treatment.
Possible	The AE may be related to treatment.
Probable	The AE is likely related to treatment.
Definite	The AE is clearly related to treatment.

- **CAEPR (Comprehensive Adverse Events and Potential Risks List):** An NCI generated list of reported and/or potential AEs associated with an agent currently under an NCI IND. Information contained in the CAEPR is compiled from the Investigator's Brochure, the Package Insert, as well as company safety reports.
- **CTCAE:** The NCI Common Terminology Criteria for Adverse Events provides a descriptive terminology that is to be utilized for AE reporting. A grade (severity) is provided for each AE term.
- **Hospitalization (or prolongation of hospitalization):** For AE reporting purposes, a hospitalization is defined as an inpatient hospital stay equal to or greater than 24 hours.
- **Life Threatening Adverse Event:** Any AE that places the subject at immediate risk of death from the AE as it occurred.

Rev. Add1

Rev. Add3

- **Serious Adverse Event (SAE):** Any adverse event occurring at any dose that results in **ANY** of the following outcomes:
 - Death
 - A life-threatening adverse event
 - Inpatient hospitalization or prolongation of existing hospitalization (for \geq 24 hours).
 - A persistent or significant incapacity or substantial disruption of the ability to conduct normal life functions.
 - A congenital anomaly/birth defect.
 - Important Medical Events (IME) that may not result in death, be life threatening, or require hospitalization may be considered a serious when, based upon medical judgment, they may jeopardize the patient or subject and may require medical or surgical intervention to prevent one of the outcomes listed in this definition.

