5.2.10 Additional instructions, requirements and exceptions for protocol
EA5152

Additional Instructions

For instructions on how to specifically report events that result in persistent or significant disability/incapacity, congenital anomaly, or birth defect events via CTEP-AERS, please contact the AEMD Help Desk at [contact] or [contact]. This will need to be discussed on a case-by-case basis.

Reporting a death on study: A death occurring while on study or within 30 days of the last dose of treatment requires both routine and expedited reporting, regardless of causality. Attribution to treatment or other cause must be provided.

NOTE: A death due to progressive disease should be reported as a Grade 5 "Disease progression" under the System Organ Class (SOC) "General disorder and administration site conditions". Evidence that the death was a manifestation of underlying disease (e.g. radiological changes suggesting tumor growth or progression; clinical deterioration associated with a disease process) should be submitted.

EA5152 specific expedited reporting requirements:

- **Colitis:** Any grade 3-5 colitis that is considered treatment related must be reported in CTEP-AERS accessed via Medidata Rave within 24 hours of learning of the event, followed by a complete expedited report within 5 calendar days of the initial 24-hour report.
- **Pneumonitis:** Any grade 3-5 pneumonitis that is considered treatment related must be reported in CTEP-AERS accessed via Medidata Rave within 24 hours of learning of the event, followed by a complete expedited report within 5 calendar days of the initial 24-hour report.
- **Infusion Reactions:** Any grade 3-5 infusion reaction must be reported in CTEP-AERS accessed via Medidata Rave within 24 hours of learning of the event, followed by a complete expedited report within 5 calendar days of the initial 24-hour report.

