9.2 Study Endpoints

Main study: Progression-free survival (PFS) is defined as the time from randomization to documented disease progression (site review of imaging) or death from any cause, whichever occurs first. Patients who have not experienced an event of interest by the time of analysis will be censored at the date they are last known to be alive and progression-free. Overall survival is defined as the time from randomization to death from any cause, and patients who are thought to be alive at the time of final analysis will be censored at the last date of contact. Best objective response will be evaluated via RECIST1.1 criteria, as described in Section [6](#) of this protocol document. Toxicity will be determined using the CTCAE criteria.

Targeted therapy sub-study: This group will be evaluated by PFS, overall survival, best objective response rate, and toxicity as above.

Exploratory Imaging Correlative Study: For RECIST1.1 (central review) and irRC PFS is defined as the time from randomization to documented disease progression or death from any cause, whichever occurs first. For iRECIST, PFS is defined as the date of the time from randomization to documented disease progression (date of the documented iUPD that is followed by subsequent iCPD) or death from any cause, whichever occurs first.

For the imaging correlates, overall survival is defined as the time from randomization to death from any cause, and patients who are thought to be alive at the time of final analysis will be censored at the last date of contact. Best objective response will be evaluated for all three criteria performed by central review as defined in Section [6](#) of this protocol document.

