Cancer Treatment Variables. Clinical variables including date of diagnosis, malignancy type (smoking related vs. non-smoking related, cancer stage), and treatment details (i.e. types and dates of surgery, chemotherapy, and/or radiation received), along with disease status and survival, will be captured in Medidata Rave via the parent protocol and will be available for analysis of the ancillary. Provider-assessed adverse events will also be captured via the parent protocol in Medidata Rave, using case report forms commonly used across the NCTN and using standard data elements.

Assessments

All items in Survey of Tobacco Use will be administered using the EASEE-PRO system. The advantage of our virtual electronic data capture system is that our proposed assessments will not be limited to, or dependent upon, patient trial visits. Confidential and potentially stigmatizing information can be provided without requiring direct contact with the care team.

Timing of Assessments

Given the critical questions that remain¹³ about the timing of conducting tobacco use assessments, we have carefully chosen to collect tobacco assessment data at trial enrollment, 3 and 6 month follow-up. For tobacco treatment trials, 6 month follow-up is the recommended primary outcome time point. By 6 month follow-up, most cancer treatment-related quitting activity⁶², cancer treatment initiation of therapy, and FDA-approved smoking cessation medication regimens will be completed. Adverse events during treatment will have been observed.

Statistical Considerations and Analysis Plans

The analysis plans described below are planned for a combined analysis of the data from the 8 selected ECOG-ACRIN trials. Consistency in the effects over the studies would be examined in this analysis.

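### Appendix VIII item 2 counts deaths from cancer progression as lethal treatment toxicity, because worst grade covers all event types and Section 5.2.10 codes those deaths as Grade 5 events

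*Combined protocol and SAP*

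**What the plan says.** Four places have to be read together.

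- **Coding.** Section 5.2.10 says that a death on study or within 30 days of the last dose "requires both routine and expedited reporting, regardless of causality". It adds: "A death due to progressive disease should be reported as a Grade 5" event, under the term *Disease progression*.
- **Data source.** Appendix VIII, under Cancer Treatment Variables: "Provider-assessed adverse events will also be captured via the parent protocol in Medidata Rave". The ancillary therefore uses the parent trial's routine adverse event records.
- **Derivation.** Appendix VIII, item 2, takes each patient's "worst degree toxicity across all event types and treatment visits", on a scale with "grade 5 signifying a lethal adverse event". It compares the distribution of worst grades by smoking status and by environmental exposure using exact tests, and also examines it by form of tobacco use.
- **Aim.** Section 2.5.1 seeks the effect of tobacco "on provider-reported cancer-treatment toxicity (adverse events (both clinical and hematologic) and dose modifications".

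Neither Section 2.5 nor Appendix VIII excludes the *Disease progression* term or limits the worst grade by attribution.

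**The concern.** The outcome is meant to capture harm from treatment. Under the rule as written, a patient whose worst true toxicity is grade 1 fatigue, and who dies of lung cancer while on treatment, is scored at the top of the toxicity scale.

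The error need not fall equally on the groups compared. Section 1.8 lists shorter survival among the known risks of continued smoking after diagnosis. If smokers die of their cancer sooner, more of them receive a grade 5, and the analysis could report that smoking worsens treatment toxicity when only prognosis differs.

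Elsewhere the plan keeps the two ideas apart. Appendix VIII, item 5, treats adverse events and disease progression as separate reasons for stopping treatment.

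**Working it through.** The plan states no figure on this point, so there is none to reproduce. The check is a reading of the rules, followed by an illustration of size.

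**Reading the rules**

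1. A progression death on study is reported routinely, as Grade 5, term *Disease progression* (5.2.10).
2. Routine adverse event records in Rave feed the ancillary (Appendix VIII).
3. The worst grade is the maximum over all event types, with no term removed (Appendix VIII, item 2).
4. That patient's worst toxicity grade is therefore 5, whatever toxicity occurred.

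**Scale.** The nivolumab arm quoted in Section 1.1 has a median OS of 12.2 months. With a constant hazard, the chance of death from any cause in 30 days is 1 − exp(−(ln 2 / 12.2) × (30 / 30.4)) = 0.0545. This only shows that a few per cent is plausible. It is all-cause mortality from one cited trial, not a progression-death rate for eight trials.

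**Illustration**

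*From the documents:* 1500 patients, 20% smokers (Appendix VIII, item 3), so 300 vs 1200.

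*Assumed:* a worst-grade mix before progression deaths, the same in both groups, of 5, 15, 29, 40, 10 and 1% for grades 0 to 5; and progression-death rates d of 5% in non-smokers and 5, 7.5 or 10% in smokers.

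For base proportions b(k), grades 0–4 become b(k) × (1 − d), and grade 5 becomes 0.01 × (1 − d) + d:

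- d = 5%: 0.0095 + 0.05 = 0.0595
- d = 7.5%: 0.00925 + 0.075 = 0.08425
- d = 10%: 0.009 + 0.10 = 0.109

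In the 5% group, progression deaths make up 0.05 / 0.0595 = 84% of all grade 5 scores.

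The noncentrality of the chi-square test on the six grades (5 df, critical value 11.07) is λ = 1500 × 0.2 × 0.8 × Σ (difference² / pooled proportion).

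- 7.5% vs 5%: pooled d is 0.055 and pooled grade 5 is 0.2 × 0.08425 + 0.8 × 0.0595 = 0.06445. Grade 5 contributes 0.02475² / 0.06445 = 0.00950. Grades 0–4 together contribute 0.025² × 0.99 / 0.945 = 0.00065. λ = 240 × 0.01016 = 2.44.
- 10% vs 5%: pooled d is 0.06 and pooled grade 5 is 0.0694. The contributions are 0.0495² / 0.0694 = 0.03531 and 0.05² × 0.99 / 0.94 = 0.00263. λ = 240 × 0.03794 = 9.11.

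| Progression deaths, smokers vs non-smokers | P(significant), noncentral chi-square | P(significant), simulation |
|---|---|---|
| 5% vs 5% | 5% | about 5% |
| 7.5% vs 5% | 18% | about 20% |
| 10% vs 5% | 63% | about 61% |

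True toxicity is identical in every row. In this approximation only the assumed 1% toxic-death rate matters, not how the other 99% is spread over grades 0 to 4. The chi-square test stands in for the planned exact test.

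**The case against.** **Scope.** The analysis is exploratory. Section 2.5 says each parent study's tobacco data will not be reported in its clinical study report. The other seven trials' coding rules and death rates are not shown. All of this stands, and it limits the importance of the point.

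**Timing.** Item 2 speaks of events during treatment and at treatment visits, so a progression death after the last visit may fall outside it. That also stands: deaths within 30 days of the last dose are only possibly caught. On-treatment progression deaths are not removed by this wording.

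**Dependence on a gap.** With equal progression-death rates the test keeps its level. Section 1.8 gives the direction of a gap but no size. Item 5 also compares efficacy endpoints by tobacco use, so a prognostic difference would be visible beside the toxicity result. That helps a careful reader but does not correct the toxicity outcome.

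Three stronger readings are tempting and not supported.

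- *The arm comparison in Section 9 is biased too.* Section 9.2 says only "Toxicity will be determined using the CTCAE criteria", and 9.3 names Fisher's exact test. Neither states a worst-grade rule. Silence on attribution does not show that progression deaths would be counted as toxicity there.
- *The false-positive rate is 33% or 81%.* Those figures arise, under the same assumed death rates and 1% toxic deaths, from an exact test of grade 5 against the rest. The plan compares the whole grade distribution, where the effect is diluted.
- *The main definition should be limited to treatment-related events.* Section 5.2.4 does provide for attribution ("An assessment of the relationship between the adverse event and the protocol treatment"), but Section 5.4.3 warns that toxicity from these combinations is hard to attribute. In a tobacco analysis, events blamed on smoking could be marked unrelated and dropped, hiding the effect under study.

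**Conclusion.** The point holds for Appendix VIII, item 2. As written, progression deaths reported on study, and possibly those within 30 days of the last dose, count as lethal treatment toxicity in the tobacco comparisons. This conflicts with the stated aim and can produce a false toxicity effect of smoking.

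Under the assumed rates above, the chance of a spurious finding is about 20% or 61% instead of 5%. These figures rest on an assumed prognostic gap, an assumed 1% toxic-death rate in both groups, and all eight trials coding progression deaths as this one does. They show what the rule can do and do not predict the result.

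The defect does not touch PFS, the Section 9 arm comparisons or any decision in this trial. It is an inexpensive correction to an exploratory analysis.

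**What to change.** In Appendix VIII, item 2, state that each patient's worst grade is derived after excluding the term *Disease progression*, and that progression deaths are tabulated separately by tobacco group. Before pooling, confirm how the other seven trials code such deaths and apply the same exclusion to each.

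A version restricted to events at least possibly related to treatment may be added as a sensitivity analysis, but not as the main definition.

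The cost is about one sentence. The term is already recorded, so nothing changes for sites, forms or patients. The remaining weakness is that a death coded under another term, though really due to progression, would still count. The separate table of deaths would help to reveal that.
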